UAVG	Dutch Act on Implementation of the General Data Protection Regulation; in Dutch: Uitvoeringswet Algemene Verordening Gegevensbescherming
WMO	Medical Research Involving Human Subjects Act, in Dutch: Wet Medisch-wetenschappelijk Onderzoek met Mensen

**Please add any new definitions that are used in the research protocol*

Summary

Rationale

The impact of donor and recipient sex combinations on kidney transplant outcomes has been widely studied, yet results remain inconclusive. Immunologically, female recipients of male donor kidneys face higher graft failure and mortality risks due to H-Y antigens. Another theory suggests male recipients of smaller female kidneys have worse outcomes due to nephron overload and hyperfiltration. Estrogen's protective effect against ischemia-reperfusion injury (IRI) lowers delayed graft function (DGF) incidence in female recipients, but recent research indicates higher mortality and graft loss rates for female recipients compared to males. These conflicting findings mainly pertain to deceased donor transplants.

For living donor kidney transplants (LDKT), previous study reported that male recipients of male donor kidneys had better graft survival in a study of 30,258 LDKTs from 1990-1999. Another study of 5,716 HLA-identical sibling transplants from 1985-2000 showed female recipients had better graft survival regardless of donor sex. Despite clinical advances, no large-scale studies have explored this issue in the last two decades.

Objective(s)

1. To investigate the impact of different donor and recipient sex combinations on the graft survival following living donor kidney transplantation
2. To investigate the impact of different donor and recipient sex combinations on the graft function (eGFR) following living donor kidney transplantation

Study type

Retrospective cohort study

Study population

Adult patients (n=~2000) undergoing LDKT at Erasmus Medical Center (EMC) and University Medical Center Groningen (UMCG) between January 2010 and December 2020.

Methods

Retrospective data from our transplant database were used to identify patients undergoing LDKT between January 2010 and December 2020. LDKTs were categorized into male-to-male, female-to-male, male-to-female, and female-to-female groups based on donor-recipient sex combinations. The primary outcome was death-censored graft survival. The secondary outcomes included patient survival, delayed graft function (DGF), acute rejection and graft function.

Burden and risks

N/A (no intervention involved)

Recruitment and consent

Informed consent has been waived based on the unreasonable effort due to the large size and its observational nature.

1. Introduction and rationale

The impact of donor and recipient sex combination on kidney transplant outcomes has been studied extensively, but with inconclusive results. From an immunologic perspective, the transplantation of male donor kidneys into female recipients was associated with an increased risk of graft failure and mortality due to H-Y minor histocompatibility antigens.^{1,2} Another theory, based on nephron overload and hyperfiltration, suggests that male recipients of female donor kidneys tend to experience worse outcomes due to the smaller size of female kidneys.³ Additionally, the influence of sex hormones has also been explored. Aufhauser et al.⁴ found that estrogen acts as a protective factor against ischemia-reperfusion injury (IRI), resulting in a significantly lower incidence of delayed graft function (DGF) in female recipients compared to male recipients. However, recent research by Vinson et al.⁵ demonstrates that female recipients have higher excess mortality rates and graft loss rates than males. These findings seem conflicting, and primarily focus on deceased donor kidney transplantation.

In terms of living donor kidney transplantation (LDKT), Kayler et al.⁶ analyzed a transplant database encompassing 30,258 LDKTs between 1990 and 1999. Their study revealed a significant advantage in graft survival for male recipients of male donor kidneys compared to the other combinations. Another study involving 5,716 HLA-identical sibling kidney transplantations between 1985 and 2000 demonstrated that female recipients tend to have better graft survival rates regardless of the donor's sex.³ Despite advancements in clinical practice, no such large-scale studies exploring this question have been conducted in the subsequent two decades.

2. Objective(s)

- I. To investigate the impact of different donor and recipient sex combinations on the graft survival following living donor kidney transplantation
- II. To investigate the impact of different donor and recipient sex combinations on the graft function (eGFR) following living donor kidney transplantation

3. Study type

3.1. Study type

Retrospective
 Prospective
 Combination Retrospective/Prospective

3.2. Single center / Multicenter

Single center
 Multicenter

3.3 Check all the applicable boxes

Medical records (re-use of data from healthcare, including AI)

Sex impact on living donor kidney transplantation

- Case report
- Re-use data from research
- Evaluations of quality of healthcare (retrospective)
- Research with additional use of residual material from regular healthcare
- Research with re-use of human material from research or existing biobank
- De novo biobank
- Phase IV research
- Healthcare evaluation research (prospective)
- Research with medical devices
- Research with In Vitro Diagnostic Tests
- Other research

4. Study population

4.1. Study population

- Adults (16 years and older)
- Minors (younger than 16 years)
- Incapacitated adults (16 years and older)
- Incapacitated minors (younger than 16 years)

4.2. Population (base)

Adult patients (n=~2000) undergoing LDKT at Erasmus Medical Center (EMC) and University Medical Center Groningen (UMCG) between January 2010 and December 2020.

4.3. Inclusion criteria

In order to be eligible to participate in this study, a subject must meet all of the following criteria:
Adult patients undergoing LDKT at EMC and UMCG between January 2010 and December 2020.

4.4. Exclusion criteria

Patients who lost the follow-up.

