4.5. Sample size calculation

To acquire enough data to make the research results robust, the estimated subject number is ~2000 patients.

5. Methods

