5.1. Research methods

Retrospective data from our transplant database were used to identify patients undergoing LDKT between January 2010 and December 2020. LDKTs were categorized into male-to-male, female-to-male, male-to-female, and female-to-female groups based on donor-recipient sex combinations. The primary outcome was death-censored graft survival. The secondary outcomes included patient survival, delayed graft function (DGF), acute rejection and graft function.

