7.1 Main study parameters/endpoints

The primary outcome was death-censored graft survival.

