7.2 Secondary study parameters/endpoints

The secondary outcomes included patient survival, delayed graft function (DGF), acute rejection and graft function. Graft function is defined by estimated glomerular filtration rate (eGFR) using the Chronic Kidney Disease Epidemiology Collaboration (CKD-EPI) equation.

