7.3 Other study parameters

Patient age, gender, medical history, surgical details and follow-up data.

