7.4 Analysis

Continuous variables were reported as medians with interquartile ranges (IQRs), and categorical variables were reported as frequencies with percentages. The Kruskal-Wallis test was used to compare continuous variables, and the chi-squared test was used to compare categorical variables. Kaplan-Meier curves and the log-rank test were used to compare patient and graft survival rates. Cox-regression was performed to identify the risk factors for death-censored graft failure. Variables with a p-value < 0.1 in the univariate analysis were included in the multivariate analysis. The proportional hazards assumption was evaluated through Schoenfeld residuals. A two-sided p-value < 0.05 was considered statistically significant. All statistical analyses were conducted using R version 4.2.2.

8. Ethical considerations

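### The only exclusion criterion removes patients lost to follow-up without defining loss, so eligibility depends on a post-transplant event and follow-up that could be censored is deleted

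*Combined protocol and SAP*

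**What the plan says.** Cohort entry is fixed by the transplant (section 4.3): "Adult patients undergoing LDKT at EMC and UMCG between January 2010 and December 2020". The whole of section 4.4 is one exclusion: "Patients who lost the follow-up". No time point, minimum duration or definition of loss is attached to it.

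The primary endpoint is a time-to-event outcome (section 7.1): "The primary outcome was death-censored graft survival". Patient survival is among the secondary outcomes in section 7.2. Section 7.4 states that "Kaplan-Meier curves and the log-rank test were used to compare patient and graft survival rates" and adds Cox regression for death-censored graft failure. The groups compared are the four donor-recipient sex combinations (section 5.1).

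Follow-up otherwise appears only as a type of data. Section 7.3 lists "Patient age, gender, medical history, surgical details and follow-up data" without saying which dates are held. Censoring at death is stated for the primary outcome. A rule for patients lost to follow-up and an end-of-follow-up date are not.

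**The concern.** A patient can be lost only after transplantation, so this criterion decides membership of the cohort by a post-baseline event. The planned survival methods are built for incomplete follow-up: a patient seen for six years and then lost contributes six years and is censored. Deleting that patient discards the six years. If those who had an event before any loss stay in, time is removed from the denominator and no events from the numerator.

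The wording allows several cohorts:

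- **A.** Lost before graft failure, death or cut-off; patients with a graft failure are kept.
- **B.** Lost at any time before death or cut-off, whether or not the graft had failed. This is plausible because patient survival is also an endpoint.
- **C.** No post-transplant record at all.
- **D.** Less than some minimum follow-up. This is possible, but it was not assessed here.

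Two analysts working from the same sentence could build different cohorts and report different graft-failure and death rates. If loss also differed between the sex combinations, the comparison that is the study's objective would be affected.

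**Working it through.** **Plan's own figure.** The only number nearby is the sample size in section 4.5: "the estimated subject number is ~2000 patients". It cannot be reproduced, because no effect size, event rate, power or loss rate is given. The point does not rest on it.

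**Inputs, all assumed; none is in the documents.** Graft failure 1.5%/yr, death 2%/yr, random loss c between 0.1% and 3%/yr, constant hazards, and potential follow-up A uniform over 4 to 15 years.

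**Formula.** Let h be the hazard of the events that end follow-up: 0.015 + 0.020 = 0.035 for graft failure under A, and 0.020 for death under B. Let k = h + c.

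- Observed person-time per patient: P = mean over A of (1 − e^(−kA))/k.
- Person-time belonging to lost patients: Q = mean over A of c[(1 − e^(−kA))/k² − A·e^(−kA)/k].
- Proportion excluded: c·P.
- Deletion removes Q of the time and no events, so the rate is multiplied by 1/(1 − Q/P). Censoring leaves it at 1.

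Example (A, graft failure, c = 0.03): k = 0.065, P = 6.910 years, Q/P = 0.136. The ratio is 1/(1 − 0.136) = 1.157, and 0.03 × 6.910 = 20.7% of patients are excluded.

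| Assumed loss/yr | Excluded (A) | Person-time discarded (A) | Graft-failure ratio (A) | Death ratio (A)* | Death ratio (B) |
|---|---|---|---|---|---|
| 0.1% | 0.8% | 0.5% | 1.005 | about 1.01 | 1.005 |
| 0.25% | 2.0% | 1.2% | 1.012 | about 1.01 | 1.013 |
| 0.5% | 3.9% | 2.4% | 1.025 | 1.02 | 1.026 |
| 1% | 7.6% | 4.7% | 1.050 | 1.05 | 1.052 |
| 2% | 14.5% | 9.3% | 1.102 | 1.10 | 1.106 |
| 3% | 20.7% | 13.6% | 1.157 | 1.15 | 1.164 |

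*By simulation under the same assumptions, with deaths followed after graft failure. An eligibility rule fixes one cohort for every endpoint, so cohort A affects patient survival too.

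**Graft failure under B.** Removal does not depend on whether the graft failed, so under random loss failures and time go in proportion and the ratio is 1.00. If the loss hazard changes after graft failure (baseline loss 1-3%/yr), the ratio becomes 1.03-1.08 when loss halves and 0.96-0.88 when it doubles.

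**On the survival scale.** True 10-year graft failure is 1 − e^(−0.15) = 13.9%. Under A it becomes 14.3% at 0.5% loss and 15.9% at 3%. True 10-year mortality is 1 − e^(−0.20) = 18.1%. Under B it becomes 18.6% and 20.7%. With lost patients retained and censored, simulated rate ratios are about 1.00 throughout.

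**Group comparison.** With equal loss the inflation nearly cancels: a true HR of 1.50 is estimated at 1.49-1.50. With unequal loss and a true HR of 1.00, graft failure under A gives 1.102/1.050 = 1.05 for loss of 1% v 2%/yr and 1.157/1.050 = 1.10 for 1% v 3%/yr. Death under B gives about the same.

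The simulated type I error of the four-group log-rank test used 500 patients per group (assumed). With loss of 1, 1, 2, 2%/yr it is 5.9% (graft failure, A) and 6.2% (death, B). With 1, 1, 3, 3%/yr it is 8.7% and 10.1%.

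**The case against.** The best defence is that the authors meant patients with no usable record. Survival methods presuppose right-censoring, and censoring at death is already part of the primary endpoint, so reading C is at least as natural as A or B, and under C little or nothing is lost. Sections 4.2 and 4.5 both give about 2000, one as the base population and the other as the estimated number of subjects. That fits few exclusions better than a fifth of the cohort. Both figures are approximate, so this is suggestive only, and the text of 4.4 does not say C.

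It is also fair that every loss rate above is assumed. At 0.1% per year the effect is negligible, and nothing in the documents rules that out. Nor does deletion always overstate the true rate: it raises the estimate above the censored one under A, but whether that exceeds the truth depends on how lost patients fare. Censoring has the same weakness if loss is informative. These points limit the size, not the defect in wording.

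A reader might infer that the sex-combination comparison is biased. The documents do not support that. Bias there needs loss to differ between groups, and no loss rate is given, overall or by group. Loss differing only by recipient sex would leave donor-sex contrasts within recipient sex unbiased. A twofold difference moves type I error only to about 6%.

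A reader might also infer that the plan has no censoring rule at all. That goes too far: what is missing is the rule for lost patients and the end date.

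**Conclusion.** The point holds, and it should be fixed. Section 4.4 is undefined, makes eligibility depend on a post-transplant event and, read literally, deletes follow-up that the planned analyses can use. Those are facts of the text and need no assumption.

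The consequence depends on the reading. Under A, graft-failure and death rates are both overstated if loss is non-informative. Under B, the death rate is overstated and the graft-failure rate is not. Under C, the effect is small. The inflation figures illustrate the mechanism under assumed constant hazards and random loss; they are not estimates for this study. Bias in the sex-combination comparison is possible, not demonstrated.

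**What to change.** State the end-of-follow-up date and replace section 4.4 with: *Patients lost to follow-up are retained and censored at the date of last known graft status (date of last contact for patient survival); only transplants with no post-transplant record are excluded.*

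Report the numbers excluded and lost by sex combination and centre. Excluding transplants with no record is still selection on a post-transplant fact, so those counts are needed. State that censoring assumes non-informative loss, and add a sensitivity analysis if loss is high or unequal between groups. This wording covers the time-to-event outcomes only; delayed graft function, acute rejection and eGFR need their own stated assessment windows.

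The cost is an amendment submitted to the review committee under section 12, with approval before implementation if it is judged substantial; the documents do not settle whether it would be. Last-contact and last-graft-status dates may have to be extracted. No new patients or procedures are needed.

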4.5. Sample size calculation

To acquire enough data to make the research results robust, the estimated subject number is ~2000 patients.

5. Methods

5.1. Research methods

Retrospective data from our transplant database were used to identify patients undergoing LDKT between January 2010 and December 2020. LDKTs were categorized into male-to-male, female-to-male, male-to-female, and female-to-female groups based on donor-recipient sex combinations. The primary outcome was death-censored graft survival. The secondary outcomes included patient survival, delayed graft function (DGF), acute rejection and graft function.

5.2. Standard clinical care versus extra for research

No extra intervention are applied on the patients due to its retrospective observational nature.

5.3. Burden and risks

Not applicable because of no intervention in this study.

5.4. Medical device(s) / In vitro diagnostic tests

Not applicable because no medical device is involved in this study

6. Incidental findings

6.1. Chance of incidental findings

Is there a chance of incidental findings?

Yes
 No

6.2. Procedures

Not applicable, there is no change of incidental findings.

7. Statistical analysis

7.1 Main study parameters/endpoints

The primary outcome was death-censored graft survival.

7.2 Secondary study parameters/endpoints

The secondary outcomes included patient survival, delayed graft function (DGF), acute rejection and graft function. Graft function is defined by estimated glomerular filtration rate (eGFR) using the Chronic Kidney Disease Epidemiology Collaboration (CKD-EPI) equation.

7.3 Other study parameters

Patient age, gender, medical history, surgical details and follow-up data.

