8.1 Regulation statement

The study will be conducted according to the principles of the Declaration of Helsinki (64th World Medical Association General Assembly, Fortaleza, Brazil, October 2013). The following guidelines also apply to this study;

- Gedragscode Gezondheidszorgonderzoek 2022.
- Privacy regulation of participating hospitals
- EU General Data Protection Regulation and the Dutch Act on Implementation of the General Data Protection Regulation (in Dutch: Uitvoeringswet 'Algemene Verordening Gegevensbescherming' (UAVG)).

This study has been exempted by the Medical Research Ethics Committee (MREC); in Dutch: Non-WMO Review Committee (NWTC). Following review of the protocol, the MREC concluded this study is not subject to the Medical Research Involving Human Subjects Act (WMO). They concluded that the study is a medical/ scientific research, but no patients are subjected to procedures or are required to follow rules of behavior.

8.2 **Informed consent**

Will the subjects be asked for informed consent?

- Yes (*Upload Participant Information Letter and Informed Consent*)
- No, consent already given in previous study (*Upload Participant Information Letter and Informed Consent previous study*)
- No, this research will be performed under the exception consent (*Upload form Care for data Template, in Dutch: Formulier uitzondering toestemming*)
- Other (e.g. partly, indirectly) *Please describe the situation.*

8.3 **Recruitment and informed consent procedures**

Not applicable, patients will not be asked to consent to their data being used for the current study.

8.4 **Exception consent**

All cases in the transplant database have already provided informed consent for their data to be shared with the Dutch Transplant foundation for future research. The informed consent is asked before a recipient is placed on the transplant waiting list.

9. **Handling and storage of data / images / sound recordings / photos / film recordings**

9.1 **Data / images / sound recordings / photos / film recordings**

Patient clinical data, including demographics, surgical information and follow-up information, will be used. These data are obtained for regular healthcare purposes.

9.2 **Privacy protection**

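### The plan does not commit to controlling donor age, donor-recipient relationship or HLA mismatch, and its p < 0.1 screen can drop them even if collected

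*Combined protocol and SAP*

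**What the plan says.** The first objective in section 2 is causal in tone: "To investigate the impact of different donor and recipient sex combinations on the graft survival following living donor kidney transplantation". Section 5.1 defines the exposure at the level of the pair: "LDKTs were categorized into male-to-male, female-to-male, male-to-female, and female-to-female groups based on donor-recipient sex combinations". The primary endpoint in 7.1 is death-censored graft survival.

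The remaining variables are given in one line in 7.3: "Patient age, gender, medical history, surgical details and follow-up data". Section 9.1 describes the data in similar terms: "Patient clinical data, including demographics, surgical information and follow-up information, will be used". Donor sex is the only donor characteristic used anywhere in the plan, and it serves only to form the four groups. Donor age, donor-recipient relationship, HLA mismatch and body size are not named as covariates in any section.

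For the analysis, section 7.4 says "Kaplan-Meier curves and the log-rank test were used to compare patient and graft survival rates", which is an unadjusted comparison. Adjustment comes only through a Cox model described as a search for risk factors, with this entry rule: "Variables with a p-value < 0.1 in the univariate analysis were included in the multivariate analysis". No covariate is prespecified, and nothing states that sex combination itself stays in the model.

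The background in section 1 touches on two of the missing factors. It cites a cohort of HLA-identical siblings, and it reports the theory that "male recipients of female donor kidneys tend to experience worse outcomes due to the smaller size of female kidneys".

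**The concern.** In living donation, the sexes of donor and recipient are not independent of who donates to whom. Most spousal pairs are of opposite sex, so they fall mainly into the male-to-female and female-to-male groups. Spouses are usually genetically unrelated, so relationship tends to bring HLA mismatch with it. Donor age may also differ between groups. The direction is not obvious, because related donors include both parents and siblings. This is structural reasoning; the documents report no group-level data.

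If any of these factors affects graft loss and differs between the groups, part of its effect will be read as an effect of sex combination. The log-rank test cannot prevent this. The Cox model prevents it only if the factor is collected and then passes the screen. The plan guarantees neither. The screen asks whether a variable predicts the outcome significantly in this sample. Confounding control depends on a different question: whether leaving the variable out shifts the exposure coefficient.

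**Working it through.** **No document figure to reproduce.** The only design figure is about 2000 patients (section 4.5). It comes without an effect size, power or event rate, and the point does not depend on it. Everything below rests on assumed inputs.

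**1. How far could an uncontrolled factor move a true null?** Take a binary factor with hazard ratio g and prevalence p1 in one group and p0 in the other. With a true sex-combination hazard ratio of 1, the apparent hazard ratio is approximately

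[1 + p1(g − 1)] / [1 + p0(g − 1)].

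| Prevalence p1 vs p0 | g = 1.25 | g = 1.5 | g = 2.0 |
|---|---|---|---|
| 30% vs 30% | 1.00 | 1.00 | 1.00 |
| 40% vs 30% | 1.02 | 1.04 | 1.08 |
| 50% vs 30% | 1.05 | 1.09 | 1.15 |
| 60% vs 20% | 1.10 | 1.18 | 1.33 |

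Example: 60% vs 20% at g = 1.5 gives 1.30 / 1.10 = 1.18.

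A second set of inputs mimics spousal donation, with 30-50% spousal donors in opposite-sex pairs, 2% in same-sex pairs, and g from 1.2 to 1.5:

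- Low end: (1 + 0.30 × 0.2) / (1 + 0.02 × 0.2) = 1.060 / 1.004 = 1.06.
- High end: (1 + 0.50 × 0.5) / (1 + 0.02 × 0.5) = 1.25 / 1.01 = 1.24.

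Donor age can be illustrated separately. A 4-year difference in mean donor age, at a hazard ratio of 1.2 to 1.4 per decade, gives 1.2^0.4 = 1.08 to 1.4^0.4 = 1.14. Because the sign of the age difference is unknown, this factor could add to the one above or offset it.

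**2. If such a factor is collected, does it reach the model?** With d events, prevalence p and a two-sided screen at 0.10, the Schoenfeld approximation gives

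P(entry) = Φ( ln g × √(d p (1 − p)) − 1.645 ).

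For g = 1.25, p = 0.30, d = 200 (10% of 2000): ln 1.25 × √42 = 0.2231 × 6.481 = 1.446, and Φ(1.446 − 1.645) = Φ(−0.199) = 0.42.

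| g | 100 events | 200 events | 300 events |
|---|---|---|---|
| 1.25 | 27% | 42% | 55% |
| 1.5 | 58% | 84% | 94% |
| 2.0 | 94% | >99% | >99% |

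**3. Reading the two tables together.** A strong factor passes the screen if it has been collected, so its danger lies in not being collected. A modest factor (g = 1.25) is more likely than not to be dropped at 100 or 200 events. Its own bias is then limited: at most 1.10 in the first table. The upper end of the bias range is therefore mainly a question of naming the fields. The screen is a further and smaller leak, and it can act on several factors at once.

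**The case against.** The strongest reply is that 7.3 is a line of broad headings and not a closed list. It cannot be exhaustive, because the exposure needs donor sex and the line does not name that as a donor item. Medical history, surgical details and demographics could hold several of the factors. Section 7.4 bars no donor variable from the Cox model. The data management plan and data transfer agreement in the attachment list may contain a full variable list that is not visible here. All of this stands. It means the documents do not show that the data are absent, and naming fields in 7.3 would alone be only a matter of detail. It does not answer the point about 7.4, where a stated rule decides adjustment and can discard a real confounder.

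A reader might go further and infer that the sex-combination effect is confounded. The documents do not support that. They report no distribution of relationship, HLA match or donor age by group, and with equal prevalence the bias is nil.

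A reader might also infer that, without body size, the study fails to test its own mechanism. Testing nephron overload is not an objective; it is one of several theories in the background. Under that theory size lies partly on the pathway from donor sex to outcome, so leaving it out does not by itself bias a total effect.

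Finally, a reader might turn the apparent hazard ratios into a false-positive rate by comparing all opposite-sex with all same-sex pairs. That is not the planned test, which compares four groups, and it overstates the rate.

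**Conclusion.** The point holds as a gap in commitment, not as a demonstrated bias. The plan seeks the impact of a pair-level exposure. It names no donor factor beyond sex, and its only adjustment rule is a significance screen that does not guarantee entry of donor age, relationship or HLA mismatch.

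The size is unknown from the documents. On the assumed prevalences and hazard ratios above, it runs from nil to an apparent hazard ratio of about 1.2-1.3 under a true null. The direction for donor age is not known. The 42% chance of entry rests on an assumed hazard ratio of 1.25, 30% prevalence and 200 events. With a hazard ratio of 2.0 the screen would rarely fail.

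The change should be made: without it, a reported difference between groups cannot be attributed to sex combination with any confidence, and the cost is small.

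**What to change.** **Section 7.4.** For the sex-combination model, replace the p < 0.1 screen with a prespecified covariate set, chosen on subject-matter grounds and forced in regardless of p-value. Include at least donor age, relationship (related / spousal / other unrelated) and HLA mismatch. State that sex combination is always in the model.

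**Size.** Keep the donor/recipient size ratio out of the main model and say that this model targets the effect without adjustment for size. Add the ratio as a secondary step, reported as the change in the sex-combination hazard ratios.

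**Section 7.3 and data requests.** Name these fields, with donor and recipient height and weight for the size ratio, in 7.3 and in the request to each centre. First confirm that both centres hold them and that they may be used. Section 8.4 describes consent asked of recipients before wait-listing, so the basis for using donor fields should be checked. The Groningen data come under a transfer agreement (section 11), which may need its field list extended.

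**Cost.** A few more fields from existing records, assuming they are routinely held, and some missing data that will need a stated handling rule. The design and the burden on patients do not change.
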